STUDY PROTOCOL WITH SAP

TITLE

Therapeutic exercise protocol for the prevention of anterior cruciate ligament injuries in female football players with dynamic knee valgus.

DOCUMENT DATE: 30/07/2023

INTRODUCTION

In recent years there has been an exponential growth of women participating in team sports such as football. Around 29 million footballers worldwide are women. In addition, the numbers are constantly growing with an estimated 51% increase in the number of registered players, as is the interest of the female society in this sport¹. The popularity and visibility of women's football is associated with an increase in the number of lower extremity injuries, especially with a high risk of knee injuries. Of all the knee injuries that can occur, women are particularly susceptible to anterior cruciate ligament (ACL) injuries. The ACL plays an important role in knee kinematics². It stabilizes the joint in full extension, prevents rotational loads and anterior displacement of the tibia³. These injuries are a major current problem^{4,5} accounting for 16% to 32% of all injuries and 43% of the injury burden during the sports season⁶. Regardless of their level of participation, female footballers have between 2 and 8 times⁷ times the risk of suffering ACL injuries compared to their male counterparts⁵ performing similar training^{8,9,10}. Injury incidence rates among female soccer players range from 1.1 to 3.1 injuries per 1000 hours of training and from 12.6 to 23.6 injuries per 1000 hours of play over the past decade¹.

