5. To analyze the perceived satisfaction rates of the athletes, using the SF-12 questionnaire after the intervention.
6. Know the effective dosage of a specific protocol for the prevention of ACL injuries.

PICO Question

In soccer players with DKV... Does a specific training protocol reduce the risk of ACL injuries compared to the conventional program?

Study hypothesis

A comprehensive and specific 12-week training protocol for the 2023-2024 season will significantly reduce the risk of ACL injuries compared to conventional training for female soccer players with DKV.

METHODOLOGY

Ethical documents and prior registration

This study has the Authorization of the Ethics Committee of the Responsible Research Office of the Miguel Hernández University of Elche for the 2022/2023 academic year and will be registered as a clinical trial in the clinicalTrials platform.

Studio Design

The study is designed as a randomized and controlled, double-blind, unicentric and parallel group clinical trial protocol that will be carried out with the female players of Elche CF and Intercity CF in the province of Alicante. The recommendations of the SPIRIT guide³⁶ have been followed for the realization of this study. Annex I.

Before starting the study, they will be provided with a written informed consent that they must sign to record their intention to participate in it, being able to revoke it at any time and accepting the conditions that will appear in the document (Annex II). They will be randomly assigned to a conventional fitness training program or a specific training protocol for 12 weeks. This study will consist of 3 time measurement points, the first prior to the intervention, the second at the end of the 6-week period of intervention and the last at 4 weeks after its completion. The study schedule and flowchart are in Annex III and IV, respectively.

Participants

The recruited population will be formed by the 44 elite players (22 per team) with a federative record belonging to the first senior team of Elche CF and Intercity CF of the province of Alicante of the national women's football league during the 2023-2024 season, where three weekly training sessions of one hour each are carried out. Prior to the collection of data, permission will be requested from the Club and the coach of both teams to carry out the study at the Martínez Valero Stadium in Elche. In the same way,

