First, qualitative variables will be described with frequencies and percentages. For these variables, hypothesis tests will be performed using the Chi-squared test. On the other hand, quantitative variables will be expressed with median and interquartile range (IQR) or with mean, standard deviation and confidence interval (95% CI). It should be verified that the data follow a normal distribution with the Shapiro Wilk test to test this hypothesis. If it were not met, a nonparametric test such as the Mann-Whitney test would be performed. If, on the other hand, it follows a normal distribution, an ANOVA test will be carried out to contrast the mean difference and assess whether or not the results of the clinical trial have been significant. A level of bilateral statistical significance (limit for judging a result as statistically significant) of $\alpha = 0.05$ shall be established for all hypothesis contrasts. The data will be analyzed with the statistical program SPSS.

Budget estimate

The budget available for this study is limited to material costs, since we have the collaboration of the team of physiotherapists from several clinics in the province of Alicante. Therefore, we will select, from among those who are willing to collaborate, both the evaluating and sports physiotherapists for the study. In addition, they will provide much of the materials needed to conduct the study. If, on the other hand, the collaborating clinics did not have all the necessary material, the cost of more specific devices

such as the mDurance surface EMG (€ 5,500 approx.) and the BMS force platform (€ 3,000 approx.) should be included in the budget.

FUTURE EXPECTATIONS OF THE STUDY

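### ACL injury, the subject of the main hypothesis, has no named analysis; read as yes/no it gets an unspecified Chi-squared test, no effect estimate with an interval, and no rule for few or zero events.

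*Combined protocol and SAP*

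**What the plan says.** The Main objective, the PICO question and the Study hypothesis are all about ACL injury; the hypothesis is that the protocol "will significantly reduce the risk of ACL injuries compared to conventional training for female soccer players with DKV".

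The Statistical analysis section assigns methods by type of variable and does not mention ACL injury. For one type, "qualitative variables will be described with frequencies and percentages", and then "For these variables, hypothesis tests will be performed using the Chi-squared test". No continuity correction, exact test or small-count rule is given. The 95% CI appears only in the sentence on the other type: "quantitative variables will be expressed with median and interquartile range (IQR) or with mean, standard deviation and confidence interval (95% CI". One threshold, two-sided 0.05, covers all tests.

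Study variables and measurements says only that the number of injuries in both groups will be recorded in a spreadsheet.

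**The concern.** Whether a player has an ACL injury is naturally a yes/no outcome, and the plan's only test for that type is Chi-squared. About 22 players per arm followed for 12 to 16 weeks will produce very few ACL injuries. Three things follow. The test may have nothing to work on. A p-value without an interval does not show how much benefit or harm remains possible. And because no version of the test is named, it could be chosen after the data are seen. This is about the form of the answer to the main question; the lack of power is a separate matter.

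**Working it through.** **The plan's own figure.** Sample size bases the trial on a difference in means of 1 SD with 90% power: n per arm = 2 × (1.960 + 1.282)² / 1² = 21.01, rounded up to 22, so 44 in all; 44 × 1.10 = 48.4, stated as 48. This reproduces. ACL events play no part in it.

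**Expected ACL injuries.** Inputs from the documents:
- "Injury incidence rates among female soccer players range from 1.1 to 3.1 injuries per 1000 hours of training", and 12.6 to 23.6 per 1000 match hours (Introduction). Both are rates for all injuries.
- A 16-32% share of all injuries (Introduction), read as the ACL share.
- 44 players with three one-hour sessions a week (Participants), over 12 weeks, or 16 to the last measurement (Studio Design).

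Assumption, not in the documents: 6 to 16 matches per club, 11 players on the pitch for 1.5 h, so 2 × 11 × 1.5 = 33 player-hours per match for the two clubs.

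Expected = (44 × 3 × weeks × training rate + 33 × matches × match rate) / 1000 × share.
- Lowest: (1584 × 1.1 + 198 × 12.6) / 1000 × 0.16 = (1.742 + 2.495) × 0.16 = 0.68 in both arms, 0.34 per arm.
- Highest: (2112 × 3.1 + 528 × 23.6) / 1000 × 0.32 = (6.547 + 12.461) × 0.32 = 6.08 in both arms, 3.04 per arm.

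Extreme exposure: 24 players per arm, all playing a full match every week for 16 weeks, with every rate at its top, gives (1152 × 3.1 + 576 × 23.6) / 1000 × 0.32 = 5.49 per arm. With the 51% reduction quoted in the Justification, the mean of the two arms is 5.49 × (1 + 0.49) / 2 = 4.09.

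**Chance of no injury at all** (Poisson, no effect): exp(-0.68) = 51%; exp(-6.08) = 0.2%. With 0 v 0 the expected injury cells are 0 × 22 / 44 = 0, so the statistic divides by zero.

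**What an interval adds** (22 per arm, Newcombe):
- 0 v 0: each Wilson upper limit is 3.84 / (22 + 3.84) = 0.149, so the risk difference interval is -14.9 to +14.9 points.
- 1 v 2: Pearson p = 0.55. Wilson limits are 0.008-0.218 and 0.025-0.278, and the difference is -0.045. Lower limit: -0.045 - √(0.037² + 0.187²) = -0.236. Upper limit: -0.045 + √(0.173² + 0.066²) = +0.139.

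**Version of the test, 0 v 4 at 22 per arm:**
- Pearson: 44 × 88² / (4 × 40 × 22 × 22) = 4.40, p = 0.036.
- Yates: 44 × (88 - 22)² / 77440 = 2.475, p = 0.116.
- Fisher: 2 × C(22,4) / C(44,4) = 2 × 7315 / 135751 = 0.108.

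For 1 v 6 the three are 0.039, 0.099 and 0.095.

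**How often the version matters.** Summing binomial probabilities over all tables at 22 per arm, Pearson and Fisher disagree at 0.05 with probability 0.04% (0.34 expected per arm) to 3.0% (3.04 expected) under no effect, and 0.03% to 5.9% with a 51% reduction. Pearson and Yates disagree in at most about 9%.

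**Size of uncorrected Pearson** (same enumeration, equal risks): maximum 5.19%, at a risk of 0.17; 0.4% at a risk of 0.03.

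**Boschloo as a candidate.** Its p-value is the largest probability, over a common risk, of tables with a Fisher p no larger than the one observed, with the arm sizes fixed. For 0 v 4 this is 0.058 and for 1 v 6 it is 0.0497. Over tables with 0 to 10 injuries per arm, its verdict matches uncorrected Pearson in all but 0 v 4. The Newcombe interval for 0 v 4, -38.5 to +0.2 points, also just includes zero. Code that fixes the wrong margin (the injured and uninjured totals) returns 0.047 for 0 v 4, so the arms must be set as the fixed margin.

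**The case against.** The strongest reply is that the assignment to Chi-squared is inferred. That is true: no sentence makes it, and a recorded number of injuries could be treated as quantitative, which would lead to Mann-Whitney or ANOVA. This is itself a reason to specify the analysis. Frequencies and percentages are also planned, so the result would not be a p-value with nothing beside it; what is missing is an effect estimate with an interval.

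A reader might infer that the large-sample p-value is invalid at these counts. The calculations do not support that: the size never exceeds 5.2% and is well below 5% when events are rare. A reader might also infer that the verdict generally turns on the version of the test. It does so only in a few borderline tables.

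A reader might take the phrase "assess whether or not the results of the clinical trial have been significant" as the rule for ACL injury. It closes the ANOVA sentence for normally distributed quantitative variables and says nothing about injury.

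Nor do the documents' rates alone give fewer than five injuries per arm. That needs an assumed match exposure and the 16-32% read as the ACL share, and it fails in an extreme corner.

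Finally, Randomization and blinding assigns whole teams by coin toss, one per arm. Any player-level test or interval ignores this. That objection stands and limits what the fix can deliver.

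**Conclusion.** The point holds as a gap in specification. The outcome of the main hypothesis has no named analysis, and on the natural reading it gets an unspecified Chi-squared test that may not be computable and no effect estimate with an interval. Under the stated assumptions, 0.3 to 3.0 ACL injuries are expected per arm, with a 0.2% to 51% chance of none in the trial. Screening for DKV within two squads totalling 44 players could make the numbers smaller. The missing interval and the zero-event case carry the weight. The choice of test version is secondary: at most about 6% disagreement for Pearson against Fisher and 9% against Yates.

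**What to change.** In the Statistical analysis section:
- Define the outcome as players with at least one ACL injury out of all players, per arm.
- Make the risk difference with a 95% CI the main result, naming one method (Newcombe or Miettinen-Nurminen), and report it also when no injury occurs.
- Name one test suited to small counts in advance, for example Boschloo with the arm sizes as the fixed margin, and give no p-value at zero events.
- Say that the interval governs the wording and that p > 0.05 will not be read as no effect.
- State that the player-level interval and test ignore the assignment of one whole team per arm, so the interval is a minimum statement of uncertainty.

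The cost is SAP wording and a few lines of code outside the default SPSS table. Borderline p-values become somewhat larger (0 v 4: 0.058 in place of 0.036). Trial conduct does not change, and neither does power.

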the recruitment will be carried out through a direct contact, as an interview, with the coach, the physiotherapist and the physical trainer of the participating teams.

Inclusion and exclusion criteria

The inclusion criteria will be:

- Football players registered and federated in the corresponding team.
- With an age range between 18 and 35 years.
- Minimum experience of one year playing football.
- With the presence of DKV.

The exclusion criteria will be:

- Previously injured subjects of ACL or other knee ligament injury.
- Subjects with a history of lower extremity injuries that have resulted in surgery during the six months prior to the study.
- Players with chronic illnesses that may affect test results.
- Subjects who practice other sports in the professional field.

Study variables and measurements

To record the number of injuries produced among the players of both groups at the end of the study and the frequency of weekly training, an Excel table will be used. The kinetics and kinematics of the lower extremities will also be analyzed with a motion capture system, surface EMG markers and a force platform. The LESS scoring system (Annex V) and the DVJ task will be used to identify the risk of injury during the jump-landing task and the presence of DKV among the players, respectively. In addition, we will measure their pre- and post-intervention satisfaction rates using the SF-12 questionnaire³⁸. Annex VI.

Sample size

An analysis was performed with Epidat 4.2 software to calculate the sample size required in the present study. A comparison of independent means will be performed and a standardized mean difference of 1, a significance level of 0.05, a 95% CI and a power of 90% will be considered, which determines a total sample size of 44 subjects, 22 in each group. It is necessary to consider an abandonment rate, so we will increase the sample by 10%. Therefore, the total sample size will be 48 women, 24 in each study group. Annex VII.

Randomization and blinding

Teams will be randomly assigned to one of the two groups in a simple manner and will be performed once subject selection has been completed. This assignment will be hidden and will be carried out by a person independent of the study. The randomization method will consist of the toss of a coin assigning "heads" to the intervention group and "tails" to the control group.

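### A normality test on the outcome data decides which quantity is reported, and neither analysis branch uses the baseline; one baseline-adjusted mean difference per outcome should be fixed in advance

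*Combined protocol and SAP*

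**What the plan says.** The Statistical analysis section of the combined protocol and SAP describes a two-step rule for quantitative variables. First: "It should be verified that the data follow a normal distribution with the Shapiro Wilk test to test this hypothesis". Then the route divides. If normality holds, "an ANOVA test will be carried out to contrast the mean difference". If it does not: "If it were not met, a nonparametric test such as the Mann-Whitney test would be performed".

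The section does not give the level of the Shapiro-Wilk test. It does not say whether the test is applied per variable, per visit, per arm or to residuals, and it does not fix the nonparametric alternative. The descriptive summary is left open in the same way, as median with IQR or mean with SD. No baseline covariate, change score, repeated-measures term or primary time point is named in either branch.

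Three other places bear on this:

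- The Sample size section plans on means: "A comparison of independent means will be performed and a standardized mean difference of 1", with two-sided 0.05 and 90% power, giving 22 per group.
- The Studio Design section sets three measurement points: one before the intervention and two after it begins, the last 4 weeks after it ends.
- The Intervention section has the DVJ, LESS, SF-12, lower-limb biomechanics and muscle activation measured before training starts, so a baseline value exists for each.

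**The concern.** The two branches answer different questions. ANOVA on two groups estimates and tests a difference in means. Mann-Whitney tests whether values in one arm tend to exceed those in the other, and by itself gives no mean difference. When the data choose the branch, the quantity to be reported for an outcome is unknown until the data are in, and it may not be the one on which the trial was sized.

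This matters here because the protocol aims at lasting benefit and places a visit after training ends. Judging whether an effect persists requires the same quantity at both follow-ups. The rule allows a mean difference at one and a rank comparison at the other.

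With about 22 values per arm, a Shapiro-Wilk rejection is also a poor guide to whether a mean comparison is valid. It can come from chance, or from an outcome such as LESS taking only whole-number values.

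Separately, the plan collects a baseline for its quantitative outcomes and then makes no use of it in the comparison between arms.

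**Working it through.** **1. The plan's own figure.** Inputs from the Sample size section: standardized difference 1, two-sided alpha 0.05, power 90%.

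n per arm = 2 × (1.960 + 1.282)² / 1² = 21.01, rounded up to 22, so 44 in total. This matches. Exact noncentral-t power at 22 per arm is 0.8997. The figure is therefore the power of an unadjusted comparison of two means.

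**2. How often the rule changes the test.** Simulation with 22 per arm and 3,000-4,000 replicates per setting. Assumptions, since the documents give none of these: Shapiro-Wilk at 0.05 in each arm at each visit, with Mann-Whitney used if either arm rejects; correlation between visits 0.3-0.7 for normal data, 0.5 for lognormal data and 0.7 for integer scores; integer SD 1.5-2 as a stand-in for a score like LESS.

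| Outcome shape | Sent to Mann-Whitney | Different tests at the two follow-ups |
|---|---|---|
| Normal | about 9-10% | about 16-18% |
| Normal rounded to integers, SD 2 | about 30% | about 40% |
| Normal rounded to integers, SD 1.5 | about 53% | about 48% |
| Lognormal, sigma 0.5 | about 81-82% | about 28-29% |
| Lognormal, sigma 0.8 | about 98% | about 3% |

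The unstated unit of the check matters. For the SD 1.5 score, the Mann-Whitney rate is about 53% per arm, 61% on pooled data and 30% on residuals. On residuals from a baseline-adjusted model, the check fired in only 6-7% of integer cases.

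**3. What the switch itself does to error rates.** The rule as written, compared with always using the unadjusted mean test:

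- Type I error of the two-step rule: 0.049-0.054 in the normal and lognormal settings, and about 5-6% at most overall.
- Standardized difference 1, normal data: 0.898 with the switch, 0.900 without, a loss of 0.2 points.
- Standardized difference 0.7, integer scores: 0.587 v 0.599 (SD 1.5) and 0.616 v 0.621 (SD 2), losses of 1.2 and 0.5 points. A separate run gave 0.596 v 0.608 and 0.611 v 0.612.
- Standardized difference 1, skewed data: 0.960 v 0.894 (sigma 0.5) and 0.994 v 0.885 (sigma 0.8), gains of 6.6 and 10.9 points.

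**4. What the unused baseline costs.** Adjusting for a baseline with correlation ρ multiplies the residual SD by √(1 − ρ²). In the normal approximation, power at 22 per arm is Φ(√(22/2) / √(1 − ρ²) − 1.960).

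- Unadjusted: Φ(3.317 − 1.960) = 0.913 (0.8997 by exact t).
- ρ = 0.3: √0.91 = 0.954, power 0.935. Simulated on normal data: 0.912.
- ρ = 0.5: √0.75 = 0.866, power 0.969. Simulated: 0.956.
- ρ = 0.6: √0.64 = 0.8, power Φ(4.146 − 1.960) = 0.986. Simulated for normal or integer scores: about 97-98%, against about 88-90% under the plan's rule.
- ρ = 0.7: √0.51 = 0.714, power 0.996. Simulated: 0.994.

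The simulated unadjusted mean test gives 0.89-0.90 on normal data, so the gain is about 2 to 11 points over ρ = 0.3 to 0.7. It is forgone in both branches of the plan.

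**The case against.** The strongest reply is that the rule is conventional and does little harm. It controls type I error, loses almost nothing on normal or integer data, and protects power under skew. All of that stands.

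Two stronger readings are tempting, and the documents support neither.

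- A reader might infer that the switch blocks baseline adjustment. It blocks nothing that the plan contains, because the ANOVA branch names no baseline covariate either. Nor does a nonparametric route rule adjustment out. The alternative test is left open, and a rank-based ANCOVA reaches 0.940 on normal data and 0.984 under moderate skew at ρ = 0.5 and a standardized difference of 1.
- A reader might infer that the switch costs power. A sizeable loss appears only when a baseline-adjusted analysis is compared with one that falls back on an unadjusted Mann-Whitney. Neither is the plan's rule, and the difference is the value of the baseline.

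It can also be said that the switching rates for integer scores rest on an assumed SD and an assumed unit of testing, and that force-platform, EMG and kinematic measures are not coarse integers. That is right, so those rates are illustrations for a LESS-type score and not a forecast for most outcomes. The rate of about 16-18% for exactly normal data needs no assumption about rounding, though it still assumes a check per arm and visit.

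**Conclusion.** The point holds as a matter of prespecification and efficiency. It is not a threat to validity. The reported quantity depends on the data, can differ between the two follow-ups, and need not be the mean difference on which the sample size rests. Under a check per arm and visit, the visits are tested differently in about 16-18% of trials for normal outcomes, and about 40-50% for integer scores with an assumed SD of 1.5-2.

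Type I error is not materially affected. The switch costs about 1 point of power or less for normal or integer data and gains under skew. The avoidable loss is the unused baseline: at a standardized difference of 1, about 88-90% against about 97-98% at an assumed correlation of 0.6, and on normal data about 91% at 0.3 and 99% at 0.7 with adjustment.

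All of these figures, the plan's own 90% included, treat players as independent. The Randomization and blinding section allocates two whole teams by coin toss, so team and treatment cannot be separated whichever test is used. That problem is larger and separate.

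**What to change.** In the Statistical analysis section:

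- Delete the Shapiro-Wilk step as a rule for choosing the test. Inspect residual plots descriptively if wished.
- For each continuous outcome, prespecify one analysis: the between-arm mean difference with 95% CI from a linear model with the baseline value as covariate, in the same form at both follow-ups, with a heteroscedasticity-robust or permutation p-value.
- Fix a log scale before the data are seen for variables expected to be strongly skewed, such as EMG amplitudes.
- Report a rank-based analysis as sensitivity only, and name it.

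The cost is SAP wording. No extra measurement is needed, since the baseline is already collected.

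The downside is with strongly skewed variables left on the raw scale, where a rank test can be clearly more powerful: about 99% against 95% for the adjusted mean difference at a standardized difference of 1 and lognormal sigma 0.8. The prespecified log scale is meant to deal with that, and the sensitivity analysis would show it.

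The change does not address the allocation of two whole teams. A p-value from permuting players guards against non-normality, but it still treats players as if they had been allocated individually.

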First, an invitation will be made to all the players who are part of the teams mentioned above during the 2023-2024 preseason with the aim of starting the intervention during that same season. All respondents will receive a Google survey via WhatsApp. This questionnaire will include questions about the inclusion and exclusion criteria to select the study sample of interest as well as questions about their sports background (position, dominant limb and sports experience); anthropometric measurements (age, height, BMI and weight), which will be provided by the coaches of the selected teams; and aspects related to training (frequency of weekly training and rest period). After completing the survey, three weeks prior to the start of the clinical trial, all players who agree to participate must undergo a final screening to be included in the study. This screening will consist of undergoing a qualitative analysis of the DVJ (Annex VIII), so that, through a simple visual examination, the inclusion of those players who do not present DKV can be ruled out and only those who test positive for DKV can be registered. After selecting the final number of players, a joint talk will be given to both teams to expose the dynamics of the study and the confidentiality of the data. Subsequently, pre-intervention measurements will be carried out by the evaluating physiotherapists to record the initial state of the players. These measures will be: the quantitative analysis of the DVJ, the LESS score, the initial score in the SF-12 scale, the biomechanics of the lower extremities, the muscular activation of the lumbo-pelvic complex and the lower extremity.

During the 12 weeks that the intervention will last, periodic measurements will be made. The last one will take place one month after the end of it. In addition, the players will be asked to refrain from consuming performance stimulants, tobacco or alcohol, non-steroidal anti-inflammatory drugs (NSAIDs) or analgesics 24 hours before each session, as well as strenuous exercise. As a reminder, a WhatsApp will be sent to each athlete the day before each session, indicating the time at which they will be scheduled for training the next day. The appearance of pain during the sessions will not be allowed and, if at any time it appears, the training of the player in question will be stopped immediately and recorded for further analysis.

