The intervention will consist of performing 3 weekly training sessions for 12 weeks to reach a total of 36 sessions of 30-60 minutes each. The days that will be set for training will be Mondays, Wednesdays and Fridays, leaving a rest day between sessions to ensure adequate recovery and quality training. The physical trainers will have to agree so that the training load in both groups is very similar.

Next, we will proceed to detail the intervention that will be carried out in each of the two groups of this clinical trial:

Conventional fitness training group

The players who belong to this group will maintain the usual practice of football training, so no new intervention will be applied.

Training group with a specific ACL injury prevention protocol

This protocol is based on prevention programs that use a multifaceted approach, effective in reducing the risk of ACL injuries compared to those who used only one type of exercise^{14,21,34}. A wide variety of studies defend the importance of working the muscles of the trunk, hip and knee to prevent DKV^{23,28,30}. Therefore, lumbo-pelvic stabilization training (*core* stability) that includes motor stability and strengthening of the gluteal muscles, in addition to strengthening the lower limb itself, will lead to a significant improvement in neuromuscular control of the lower extremities and trunk in addition to producing a significant decrease in DKV and valgus moments^{10,18,20,24,29,30,32}.

The proposed exercise protocol will be designed taking into account the inclusion of three main components. Annex IX:

- Lumbo-pelvic stabilization exercises.
- Lower limb strengthening exercises.
- Integration exercises (plyometrics and balance).

The exercises integrated into the programme will be organised into three phases of implementation:

- **Phase 1** (adaptation - 1st month): Its objective is that the players learn and integrate new patterns while they train.
- **Phase 2** (Proficiency - 2nd month): Aims for players to master new patterns in a controlled environment.
- **Phase 3** (performance - 3rd month): Its objective is to perform exercises in situations as specific as possible and close to the demand and explosiveness of movements typical of the pitch.

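### The analysis of continuous outcomes names no baseline covariate, response or visit although baseline is measured; adjusting for baseline is a cheap improvement on a follow-up-only comparison

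*Combined protocol and SAP*

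**What the plan says.** The Statistical analysis section sends quantitative variables through a Shapiro-Wilk test. If normality holds, "an ANOVA test will be carried out to contrast the mean difference". For the other branch it says: "If it were not met, a nonparametric test such as the Mann-Whitney test would be performed". No covariate, response, visit or time factor is named in either branch.

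The Intervention section lists what is recorded before the intervention: "These measures will be: the quantitative analysis of the DVJ, the LESS score, the initial score in the SF-12 scale", followed by lower-limb biomechanics and muscle activation. The Sample size section rests on an unadjusted two-group comparison: "A comparison of independent means will be performed and a standardized mean difference of 1".

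On visits, the Studio Design section sets three measurement points. The first precedes the intervention; the others are described as "the second at the end of the 6-week period of intervention and the last at 4 weeks after its completion". The same section gives 12 weeks of training, and so does the Intervention section: "The intervention will consist of performing 3 weekly training sessions for 12 weeks". That section also says: "During the 12 weeks that the intervention will last, periodic measurements will be made".

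On allocation, the Randomization and blinding section states: "Teams will be randomly assigned to one of the two groups in a simple manner". The two teams are the two clubs named in the design, so there is one team per arm.

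**The concern.** Specific objectives 3 to 5 rest on DVJ, LESS and SF-12, each of which is measured at baseline. As written, the plan allows a comparison of follow-up values only, a comparison of changes, or a repeated-measures ANOVA. It allows any of these at either post-baseline visit. Two things are at stake.

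- **Precision and baseline difference.** On the follow-up-only reading, which fits the independent-means sample size, data already collected are ignored. Any baseline difference between the arms that persists then stays in the treatment estimate. With two clubs allocated by a coin toss, such a difference is a realistic possibility.
- **Prespecification.** With response and visit open, both could be chosen after the data are seen. This holds on every reading of the plan.

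**Working it through.** **1. The plan's own figure.** With a standardised difference of 1, two-sided alpha 0.05 and 90% power, n per arm = 2 × (1.960 + 1.282)² / 1² = 21.01, rounded up to 22, or 44 in total. This matches the Sample size section and contains no baseline term. By noncentral t (ncp = √(22/2) = 3.317, 42 df), power at 22 per arm is 0.900.

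**2. Assumption.** The documents give no baseline to follow-up correlation r. I use 0.3, 0.5 and 0.7.

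**3. Power with 22 per arm, effect of 1 raw SD, players treated as independent.** The effective standardised effect is 1 for follow-up only, 1/√(1 − r²) for ANCOVA (41 df) and 1/√(2(1 − r)) for change scores (42 df).

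| r | Follow-up only | ANCOVA | Change |
|---|---|---|---|
| 0.3 | 90.0% | 92.4% | 78.2% |
| 0.5 | 90.0% | 96.2% | 90.0% |
| 0.7 | 90.0% | 99.5% | 98.7% |

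The Participants section gives 22 as the whole squad, before exclusions and DKV screening. At an illustrative 15 per arm, follow-up only has 75.3% and ANCOVA 79.0/86.2/95.9%.

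The Sample size section does not say which outcome or scale its effect refers to. If 1 is in change-score SDs, the raw effect is √(2(1 − r)) = 1.18/1.00/0.77. At 22 per arm, power is then 97/90/71% for follow-up only, 98/96/94% for ANCOVA and 90% for change.

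**4. Baseline difference D between the arms.**

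- If D is chance, the estimate shifts by rD (follow-up only), −(1 − r)D (change) and about 0 (ANCOVA).
- If D is a stable team difference, present at baseline and follow-up, the bias is D (follow-up only), about 0 (change) and about (1 − r)D (ANCOVA).

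**5. Simulation.** 22 per arm, unit-variance bivariate normal, no treatment effect, stable team difference D in SDs. Triplets are for r = 0.3/0.5/0.7; a single value applies to all three.

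| D | Quantity | Follow-up only | ANCOVA | Change |
|---|---|---|---|---|
| 0 | RMSE | 0.30 | 0.29/0.26/0.22 | 0.36/0.30/0.23 |
| 0.3 | Bias | 0.30 | 0.21/0.15/0.09 | 0.00 |
| 0.3 | RMSE | 0.43 | 0.36/0.31/0.24 | 0.36/0.30/0.23 |
| 0.3 | False positives | about 16% | 10.9/8.4/6.8% | about 5% |
| 0.5 | Bias | 0.50 | 0.35/0.25/0.15 | 0.00 |
| 0.5 | RMSE | 0.58 | 0.46/0.37/0.27 | 0.35/0.30/0.23 |

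ANCOVA has lower RMSE than follow-up only in all nine combinations. Outside that range the gain disappears: with D = 0 and r between 0 and 0.1, ANCOVA's RMSE is 0.304 to 0.306 against 0.302.

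**6. Cost of requiring both ANCOVA and change scores to be significant.** With D = 0 and an effect of 1 raw SD, simulated power is about 77/89/99% at 22 per arm. For r = 0.3 and 0.5 that is below the 90% of the follow-up-only test.

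**The case against.** The strongest reply is that follow-up only is the least favourable reading. Specific objective 3 and the Expected results section speak of changes, the variables section mentions satisfaction before and after the intervention, and three time points are planned. A change-score or repeated-measures ANOVA may be intended; with one follow-up visit, the group-by-time test is the same as the change-score test. On that reading the baseline data are used, and ANCOVA is not clearly better: with a stable team difference of 0.3 SD its false-positive rate is 10.9/8.4/6.8% against about 5% for change scores.

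This stands in part. A reader might infer that the plan definitely discards baseline; the documents do not support that, because they leave the response open. Equally, no change-score or repeated-measures model is written, Mann-Whitney has no time factor, and the sample size uses independent means. If change was meant, the plan still has to say so.

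A reader might also infer that follow-up only is always the weakest choice. It is not: with no team difference and r below 0.5, change scores are less precise (RMSE 0.36 against 0.30 at r = 0.3).

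Finally, the visit schedule is referred to Annex III, which is not in the text available for this review. The 6-week and 12-week wording may be settled there, but the main text needs reconciling either way.

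**Conclusion.** The point holds as a prespecification gap with a cheap remedy, and it should be acted on. Against follow-up only, ANCOVA gains 2.4 to 9.5 percentage points of power at 22 per arm for r of 0.3 to 0.7. With a stable team difference of 0.3 SD it removes 30% to 70% of the bias (0.30 down to 0.21/0.15/0.09 SD). Near r = 0 there is no gain and a trivial loss. Against change scores, ANCOVA is more precise with no team difference, about equal at 0.3 SD and worse at 0.5 SD.

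These figures rest on an assumed r and on treating players as independent, and the power gain above also on an effect of one raw SD. They are not this trial's actual power: with one team per arm, between-team variance cannot be estimated. A reader might take baseline adjustment as a repair of the design. It is not, because team and treatment remain confounded. Nor does it bear on ACL injury incidence, the main objective, which has no baseline value to adjust for.

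**What to change.** 1. Reconcile the 6-week wording in the Studio Design section with the 12-week intervention in that section and the Intervention section.
2. For each continuous outcome, name one follow-up visit for the between-group comparison.
3. Make the primary analysis an ANCOVA of the follow-up value on group and baseline value, or a mixed model over the follow-up visits with baseline as covariate and group-by-time. Report the adjusted mean difference with its 95% CI, and judge normality on the model residuals. Include no team term, since team and group coincide.
4. Prespecify a change-score analysis as a descriptive sensitivity analysis, because a stable team difference D leaves about (1 − r)D in ANCOVA. Report both estimates, but do not require both to be significant.
5. State in the SAP that none of this removes the confounding of team with treatment or applies to ACL injury incidence.

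The cost is SAP wording and one degree of freedom. The baseline measurements and SPSS are already planned, and no extra player or visit is needed. The downside is residual bias relative to change scores if the two teams differ stably.
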